5.3 Patient Preparation

Prior to implant surgery the subjects will be given a loading dose of antibiotics based on their medical history and concomitant medications. Local anesthesia will be achieved in the region by regional block or local infiltration. Conscious sedation may be added at the surgeon's discretion to help manage a patient's anxiety. The facial area will be scrubbed and the oral cavity disinfected by rinsing for 1 minute with a (0.12% chlorhexidine gluconate) antimicrobial oral rinse prior to the procedure.

Once the treatment areas are sufficiently anesthetized a crestal incision will be made and full-thickness flaps will be raised. With the aid of a surgical guide, the proposed implant sites will be identified; measurements of the alveolar ridge will be captured, using a UNC-15 periodontal probe and recorded on the implant surgery CRF.

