10.0 CRITERIA FOR SUCCESS

10.1 Grafts

The success criteria for this investigation are determined as follows: Grafts will be deemed successful if there are no reported symptoms or clinical signs or of post-application allergy, toxic reactions or evidence of gross local or systemic infections.

Histological and histomorphometric analyses will provide evidence of the relative success or failure of graft materials to enhance formation of new osseous tissue in extraction sockets. Results will be compared across experimental groups and between experimental groups and controls.

A site that fails to meet the stated criteria for success, or where the width of the ridge remains too narrow for implant insertion will be re-grafted (an offer that patients may decline). The site may receive an implant at a later date but the site will be exited from the study results.

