12.3 Outcome Endpoints

The primary efficacy parameter for implant success will be the duration of implant survival from surgical placement to 24 months post-placement across all groups. Measurement of bone height along the implant mesial and distal surfaces at 12 and 24 month follow-up evaluations will be captured from radiographic images and compared to same measurements at insertion. These measurements will be used to derive changes from baseline values.

Efficacy endpoints will include implant and prosthesis function as assessed by gingival health, bone levels and participant subjective satisfaction with the study therapy. Differences between groups will be calculated and used to determine if osseous changes and implant function are different across extraction groups and between implant groups.

Safety will be evaluated by clinical signs and symptoms of dental and medical events.

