12.4 Statistical Analysis

The general approach to statistical analysis of the study aims will be based on mixed-model analysis of variance (ANOVA). This approach will accommodate the inclusion of correlated observations due to study subjects potentially contributing measurements of more than one single tooth site to the analysis.

The sample distributions will be examined for each outcome variable. If these distributions depart substantially from normality, transformations of the data will be evaluated. If normality cannot be established by transformation, rank-based analyses will be used.

Subjects will be included as a random effect on the analyses that include multiple observations per subject. For analysis of histological data, only one tooth site per subject will be evaluated and the model will not include a random effect.

Smoking status will be included in all models in order to account for differences in response between smokers and non-smokers, and so that the analysis will correspond to the study's randomization strategy. Comparisons between smokers and non-smokers are not a primary interest in the study.

For aims in which interaction terms are of interest, significant interaction terms will be investigated using plots of least square means and separate post-hoc analyses for individual time points.

Hypothesis 1

Differences among the four groups will be evaluated by the overall F-test for the ANOVA. Pairwise comparisons among group means will be conducted using Tukey's test. Contrasts will be constructed to address each specific aim (SA).

SA-1: Compare alveolar ridge dimensions in grafted extraction sockets to that of sites healed without grafts after 8 weeks of post-extraction healing.

This SA will be addressed by comparing the combined mean of the three graft groups (FDBA/TCP, DDBA/TCP/PRP, FDBA/TCP/PDGF) with that of the CONTROL group by calculating a contrast and the corresponding F-test. Pairwise comparisons among means will be conducted using Tukey's test..

Hypothesis II

The addition of growth factors to bone grafting materials will enhance osseous and soft tissue healing.

SA-2: Assess the efficacy of bone grafting with and without enrichment with growth factors to preserve the volume of bone in extraction sockets.

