A conservative approach to power estimation was used, assuming an effective sample size of 25 observations per extraction-implant group. Power calculations utilized the Power and Precision, release 2.00, (Borenstein, 2000) and nQuery Advisor 6.0 (Janet D. Elashoff, 1995-2005) software packages. Power to detect a “medium” effect size, corresponding to a difference between group means equal to 0.50 times the within-group standard deviation (sd) was calculated. Also, the effect size detectable with 80% power was calculated. All power estimates were based on two-sided testing at the 95% confidence level.

The power for SA-1 is largely determined by the size of control group, since the primary comparison is equivalent to a t-test of the mean of the controls vs others. Thus, the assumed effective sample sizes of 25 and 75 would yield approximatey 57% power to detect a medium effect size. The difference detectable with 80% power would be approximately 0.65sd .

Power for SA-2, SA-4 and SA-5 was based on a one-way ANOVA model. The proposed sample size would provide 52% power to detect a medium effect size or 80% power to detect an effect size equivalent to a two-group difference of 0.34sd . These approximations also apply to SA-3, with the appropriate sd being the within-group standard deviation of the changes across the observation times.

The total sample size for SA-5 would be 80, or 20 per group, since this SA is based on histology, with a single extraction per participant. Power to detect a medium effect size would be 42%. The effect size detectable with 80% power is equivalent to a two-group difference of 0.72sd.

Power for SA-6 was based on linear regression with a four-category dummy variable. If stability and group each explain 10% of the observed variance, the proposed sample size would provide 80% power to detect an increment of 8.6% in explained variance for the stability*group interaction.

Power for comparison of rates of infection signs for SA-7 was based on the chi-square test for the odds ratio. The proportions in the two groups were centered on 0.50, in order to provide a conservative estimate of power. The effective sample size of 50 per group would provide 80% power to detect an odds ratio of approximately 3.2 for the association between implant type and infection.

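### Section 10.1 exits failed-graft and narrow-ridge sites from the results after randomisation; it does not keep their earlier data, and no analysis counts them by extraction group

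*Combined protocol and SAP*

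**What the plan says.** Section 10.1 (Grafts) sets a tolerability standard for success: "Grafts will be deemed successful if there are no reported symptoms or clinical signs or of post-application allergy, toxic reactions", and no gross infection. It then names the sites to be re-grafted, if the patient agrees: "A site that fails to meet the stated criteria for success, or where the width of the ridge remains too narrow for implant insertion". For these it concludes: "The site may receive an implant at a later date but the site will be exited from the study results". No width in millimetres defines a ridge that is too narrow, and the exit is not limited to particular endpoints or to data collected after re-grafting.

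The aim most exposed is SA-1 (Section 12.4): "Compare alveolar ridge dimensions in grafted extraction sockets to that of sites healed without grafts after 8 weeks of post-extraction healing". It is tested by a contrast of the three grafted groups combined against control. Section 12.5 gives its power: "Thus, the assumed effective sample sizes of 25 and 75 would yield approximatey 57% power to detect a medium effect size".

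Two sources of week-8 data come before or at the moment of exit. Section 5.1 places the CBCT scan ahead of any tissue manipulation. Section 5.3 says that, once the flaps are raised, "measurements of the alveolar ridge will be captured, using a UNC-15 periodontal probe and recorded on the implant surgery CRF".

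On safety, Section 9.1 has adverse events recorded at each visit, and Section 12.3 says: "Safety will be evaluated by clinical signs and symptoms of dental and medical events". Neither mentions extraction group.

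**The concern.** Both exit reasons arise after randomisation and could differ by arm. Hypothesis I is that grafting preserves the ridge. If that is true and control sites can exit, narrow ridges should be commoner in control, and removing them takes out the sites that carry the evidence. If only grafted sites can exit, removing the worst of them flatters grafting. The same holds if infections or reactions are commoner in a grafted arm and go with poor bone.

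The second part is that these failures are not reported by arm. The plan defines graft success, removes the failures, and then specifies no analysis that shows how many there were in each extraction group. A reader of the SA-1 and SA-2 estimates could not tell how many sites had gone, from which arm, or why.

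**Working it through.** **1. Is there a count by extraction group anywhere?**

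- SA-1 to SA-6 cover ridge dimensions, bone volume, soft-tissue healing, bone fill, histology, and the relation of healing to implant stability. None counts failures or exits.
- SA-7 tabulates infection at the implant site by collar type. A site that exits before implantation does not reach it.
- The implant survival parameter in Section 12.3 starts at placement, after the week-8 exit point.
- Section 10.1 does say "Results will be compared across experimental groups and between experimental groups and controls", but directly after the sentence on histology, which is its natural subject. Histology uses one site per participant and could not count exits at other sites.
- Section 12.4 defines no analysis population and no rule for missing data.

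**2. Reproduce the plan's SA-1 power.** Inputs from Section 12.5: effective n of 25 and 75, difference 0.50 SD, two-sided 5% level. The noncentrality is 0.50 / √(1/25 + 1/75) = 2.165 on 98 degrees of freedom. Power is 57.3%, against the stated 57%. At 0.65 SD it is 79.6%, against the stated 80%.

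**3. Illustrate the exit rule under three readings.** The documents give no exit rate, so the following are assumptions. Ridge width is normal with SD 1, with mean 0 in control and 0.50 in the grafted groups. A width cut-off c sits at the 5%, 10% or 20% point of control, and exited sites are left out of SA-1. Removing sites below c raises an arm's mean by λ = φ(c − μ) / (1 − Φ(c − μ)).

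| Cut-off at control's | c | λ control | λ grafted | Grafted sites below c |
|---|---|---|---|---|
| 5% point | −1.645 | 0.109 | 0.041 | 1.6% |
| 10% point | −1.282 | 0.195 | 0.085 | 3.7% |
| 20% point | −0.842 | 0.350 | 0.178 | 9.0% |

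- *A. All arms exit, sharp cut-off on the analysed measure:* 0.50 + λ grafted − λ control.
- *B. All arms exit, trigger correlates 0.5 with the analysed measure and has the same 0.50 SD shift:* 0.50 + 0.5 × (λ grafted − λ control).
- *C. Only grafted sites exit, sharp cut-off:* 0.50 + λ grafted.

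| Cut-off | A | B | C |
|---|---|---|---|
| 5% | 0.432 (14% too small) | 0.466 (7% too small) | 0.541 (8% too large) |
| 10% | 0.390 (22% too small) | 0.445 (11% too small) | 0.585 (17% too large) |
| 20% | 0.328 (34% too small) | 0.414 (17% too small) | 0.678 (36% too large) |

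**4. Power under A only.** Retained n is 23.8/73.8, 22.5/72.2 or 20.0/68.3, and the pooled SD of retained sites is 0.942, 0.901 or 0.835. The standardised difference is then 0.459, 0.433 or 0.393, and power is 49%, 43% or 33%. Losing the same numbers at random would leave about 55%, 54% or 49%, so under A most of the loss comes from selection. Reading A is the extreme case for understatement, so these are not expected values.

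**5. Precision of a table by arm.** Exact (Clopper-Pearson) 95% intervals at 20 participants per group: 0/20 gives 0% to 16.8%, and 2/20 gives 1.2% to 31.7%. For 0/60 in the pooled grafted groups the interval is 0% to 6.0%. Such a table can describe; it cannot rule out moderate differences.

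**The case against.** *The exit may mean less than it seems.* The same sentence speaks of a later implant. It can be read as keeping that delayed implant out of results meant for week-8 placement, with the earlier ridge and CBCT data untouched. This is plausible and the text does not exclude it. A reader might infer that the plan definitely drops these sites from SA-1. The documents support only that the literal wording does so and that nothing says otherwise.

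*Control sockets may not be covered.* The rule stands under a heading about grafts, and an ungrafted socket cannot literally be grafted again. Against that, the exit sentence speaks of a site, not a graft. The ambiguity stands, and it is why the illustration has to run in both directions.

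*The trigger is not the SA-1 outcome itself.* SA-1 concerns ridge dimensions, not width alone. No threshold is given, implant diameters run from 3.5 to 6.0 mm at the surgeon's choice (Section 5.4), and sites mix anterior teeth and premolars. This stands: a common sharp cut-off overstates the link, and reading B halves the effect.

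*Safety data are collected.* They are, and each participant's arm is known, so most events could be counted later. A reader might infer that graft-stage harms would be lost; the documents do not support that. What is missing is a planned analysis by extraction group, and a narrow ridge is not clearly an adverse event. The Manual of Procedures (Appendix E) and the case report forms were not available for this review and could address the point.

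**Conclusion.** The point holds in a limited form. Section 10.1, as worded, takes sites out of the results after randomisation on criteria that include one related to the SA-1 outcome. No text keeps the data taken before exit, and no analysis counts failures or exits by extraction group.

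The size and the direction are unknown. With an assumed true benefit of 0.50 SD, the retained difference could be anywhere from 0.33 to 0.68 SD over the three readings and the 5% to 20% cut-offs. These figures rest on normality, equal SDs, assumed exit rates and exited sites being left out of SA-1. A reader might infer from reading A that the plan is biased against grafting, with power falling to 33%. The documents do not support that as a finding, because it needs control exits, a sharp common cut-off and a 20% control exit rate, none of which they state.

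The change is worth making because the rule is easily reworded and much of the relevant week-8 data is due to be collected before a site exits.

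**What to change.** **Lead change, Section 10.1.**

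- Limit the exit to implant-stage results (SA-7 to SA-9) and to data collected after re-grafting.
- Keep all data collected up to exit, including the week-8 CBCT and ridge measurements where taken, in SA-1 to SA-5 under the randomised extraction group. SA-6 is left out because it needs a stability value at implant insertion.
- State that the infection, reaction and narrow-ridge criteria apply to sites in all four groups, including control.
- State that exited sites remain in all safety and graft-failure counts.

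**Supplement, Sections 12.3 and 12.4.** Add one descriptive table by randomised extraction group, from extraction to week 8, covering everyone who had an extraction. It should show participants with at least one Section 10.1 event, with exact 95% intervals, and sites exited by reason. Place it beside the SA-1 and SA-2 results. The table alone would show any exit-related bias but not remove it, so retaining the data comes first.

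**Cost.** A few sentences, one table and a little more analysis work, with no change to enrolment, visits or hypothesis tests. Adverse events and ridge measurements are already recorded, though coding events as allergy, toxic reaction or gross infection may need a short review of records. Intervals will be wide at 20 per group. Sites with no week-8 measurement, including those with no biopsy for SA-5, must still be reported as missing.

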10.2 Implant Survival

At each follow-up evaluation participants will be interviewed to determine if any pain or numbness has been experienced since implant placement or has developed since the previous interview. The implant sites will be examined for any evidence of implant failure including implant suppuration and erythema.

If signs or symptoms of implant failure are observed at any time during the course of the study, a periapical radiograph will be obtained and inspected for signs of radiolucency. The investigator will make assessment of implant status and if a failure is determined, will be reported on the appropriate CRF. At the investigator's discretion a medical and/or surgical attempt to rescue the implant may be made.

10.3 Implant Success

An implant will be considered successful as long as it remains immobile when tested with instrument pressure at follow-up evaluations and offers stable anchorage to a functional prosthetic attachment. A successful implant shows no evidence of fracture or signs of peri-implant radiolucency on an intraoral radiograph (using a paralleling technique strictly perpendicular to the implant bone-interface), or persistent or irreversible signs and/or symptoms of pain, infection, neuropathies or paresthesia.

11.0 COSTS TO PARTICIPANTS

11.1 Procedure Fees

No fees will be charged to participants for the, teeth extraction, socket grafting materials, implant devices, implant surgery, CBCTT scans, radiographs, photographs, bone biopsy analysis, or clinical evaluations for the entire study.

Participants will be expected to pay a **\$1,000.00 restoration fee for each study site.** This one-time-only fee will cover costs related to laboratory and materials for the fabrication of the implant restoration prosthesis. This fee is to be billed to participants prior to the initiation of any surgical procedures.

Study visits are not designed to take the place of routine dental care. Over the course of the study participants will be expected to continue with regular dental check-ups with a dentist of their choice. Should the need arise patients who do not have a regular dentist of record will be referred in the appropriate manner for any non-study related dental treatment. Costs for non-study related treatment will be charged to the participant's account or to their insurance provider in the usual manner per dental school policy and will not be paid for from the study account

11.2 Payment to Participants

Participants will be paid **\$50.00** after completing the 12-month visit and **\$50.00** after completing the final study visit at 24 months following implant insertion.

12.0 OUTCOMES AND ANALYSES

The study is structured to provide both subjective and objective data; study sites will be followed data will be captured at placement and at 12 and 24 months after implants are placed.

12.1 Objective Data

Bone biopsies preserved in the trephines and stored in formalin will be submitted to UAB's CMBD (Name of facility) Core Laboratory. Trephine core 2x6mm will be stained with hematoxylin and eosin and processed for histologic and histomorphometric analysis. Amount of bone fill and remaining bone graft (% of new bone fill, % of residual graft and % of soft tissue) material will be determined and compared across groups.

Cone Beam Computed Technology (CBCT) will be used to capture quantitative natural bone fill and bone fill following grafting applications at each extraction site.

Image analysis software will be used to capture images from the standardized radiographs taken at 12 and 24 months following implant placement. Analysis procedures will assess the implant/bone interface and measure changes in adjacent crestal alveolar bone levels over time.

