4.7 Grafting Extraction Sockets

After extractions, sockets will be grafted according to each participant's assigned randomization group.

Group-1: Each socket will be irrigated with sterile saline and allowed to heal naturally [control group].

Group-2: Each socket will be grafted with freeze dried bone allograft (FDBA) mixed with Tri-calcium phosphate (TCP) 8:2 ratio; reconstituted with sterile saline.

4.7-2a Irrigate sockets with sterile saline

4.7-2b Pack the graft into each of the study sites using mild pressure achieving complete fill of the sockets.

4.7-2c Trim a 3mm section of collaplug and secure it over the grafted areas with 4.0 Vicryl crossing mattress sutures.

Group 3: Each socket will be grafted with an 8:2 ratio FDBA/TCP graft reconstituted with Platelet Rich Plasma (PRP).

4.7-3a Collect 9-18cc blood sample from the patient via venipuncture prepare the PRP following the Cascade Fibrinet System (Appendix A)

4.7-3b Mix PRP in the FDBA.TCP graft.

4.7-3c Irrigate sockets with sterile saline.

4.7-3d Pack the graft into each of the study sites using mild pressure achieving complete fill of the sockets

4.7-3e Trim a 3mm section of collaplug and secured it over the grafted areas with 4.0 Vicryl crossing mattress sutures.

4.7-3f Once secured in place, the soak the collaplug with PRP.

Group 4: Each socket will be grafted with an 8:2 ratio FDBA/TCP graft reconstituted with recombinant platelet derived growth factor (PDGF).

4.7-4a Irrigate sockets with sterile saline.

4.7-4b Apply PDGF into the sockets completely wetting all socket walls.

4.7-4c Mix PDGF with GEM-21S (product insert Appendix B)

4.7-4d Pack the graft into each of the study sites using mild pressure achieving complete fill of the sockets

4.7-4e Trim a 3mm section of collaplug and secure it over the grafted areas with 4.0 Vicryl crossing mattress sutures.

4.7-4f Once secured in place, soak the collaplug with PDGF.

After completion of procedures the Essix retainer (if used) will be fitted and placed.

A CBCT scan will be made to include images of each study site. Prescriptions for anti-bacterial mouth wash, antibiotics, and pain relief will be provided based on individual patient needs. An ice-pack will be dispensed. Verbal and written home care instructions will be given and the patient will be scheduled for a follow-up appointment.

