This SA will be addressed using mixed-model ANOVA to compare mean bone volume among the four groups. Post-hoc pairwise comparisons will use Tukey's test. The effect of growth factors enrichment will be addressed using contrasts and F-tests to compare the mean of Group-4 with those of each of the other groups. If there is not a significant difference among the group means of Groups 1-3, the combined mean of these three groups will be compared with that of Group-4.

SA-3: Compare soft tissue healing between groups at week-1, week-2, week-4 and after 8 weeks of healing.

The analysis of SA-3 will be mixed-model ANOVA including measurements of healing made at each time points. Time will be included in the model in order to account for unequal spacing of the observational times. The statistical test that will be of primary interest will be the F-test for Group by time interaction.

SA-4: Assess quantitative bone fill across groups after 8 weeks post-extraction healing.

Qualitative bone fill will be compared among four groups using mixed-model ANOVA and the 8 week measurement only. Post-hoc pairwise comparisons will use Tukey's test.

SA-5: Compare qualitative bone fill across groups after 8 weeks post-extraction healing.

Percent new bone, percent residual graft, and percent soft-tissue will be compared among the four groups using ANOVA. For this analysis, there will be a single measurement of each of the variables per participant, so correlated observations will not be an issue in the analysis. Post-hoc pairwise comparisons will use Tukey's test.

SA-6: Assess the relationship of osseous healing and implant stability at insertion across groups after 8 weeks post-extraction healing.

This SA will be addressed by including the implant stability measure as a predictor variable in the analysis of osseous healing. The statistical test that will be of primary interest for this analysis will be the two-factor interaction of stability and group.

Hypothesis III

Laser thread-textured (LTT) dental implant will preserve longitudinal peri-implant crestal bone more effectively than implants with Resorbable blast texturing (RBT).

SA-7: Assess the efficacy of LTT and RBT surface topographies when surgically implanted into extraction sockets.

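### SA-4 compares 8-week bone fill between sockets packed with graft and ungrafted controls, with no stated CBCT rule separating residual graft from new bone

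*Combined protocol and SAP*

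**What the plan says.** - **Endpoint and analysis (12.4).** The aim reads "SA-4: Assess quantitative bone fill across groups after 8 weeks post-extraction healing". The sentence under it reads "Qualitative bone fill will be compared among four groups using mixed-model ANOVA and the 8 week measurement only", followed by Tukey pairwise comparisons. The aim says quantitative and the analysis sentence says qualitative.
- **Instrument (12.1).** CBCT "will be used to capture quantitative natural bone fill and bone fill following grafting applications at each extraction site". SA-4 itself names no instrument.
- **Starting state (4.7).** For Groups 2, 3 and 4 the instruction is "Pack the graft into each of the study sites using mild pressure achieving complete fill of the sockets". The Group 2 material is freeze-dried allograft "mixed with Tri-calcium phosphate (TCP) 8:2 ratio; reconstituted with sterile saline", and Groups 3 and 4 are described with the same 8:2 base. Group 1 sockets are irrigated with saline and left to heal.
- **What CBCT yields (5.1, 8.1).** Reconstructed images give socket volume, and Hounsfield units give the relative density of tissue at each site. No threshold, segmentation or subtraction rule is stated.
- **Where graft and bone are told apart (12.1; SA-5 in 12.4).** The 8-week trephine core is scored for percentages "of new bone fill, % of residual graft and % of soft tissue", at one site per participant.

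**The concern.** The plan treats new bone and residual graft as different things when it reads the histology core, but not when it reads CBCT fill. Groups 2-4 begin full of mineral graft and Group 1 begins with none. Any graft still present and visible at 8 weeks adds to measured fill in three groups and cannot add to it in the fourth, so the direction of the error is set by the design.

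Section 2.1 states the first study hypothesis as grafting improving the development of new bone fill. A significant SA-4 difference from control would naturally be read as support for that. Yet a grafted socket that had formed little bone could still score as well filled. Section 1.1 notes reports that graft materials may hinder natural healing, and this comparison could conceal that result.

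**Working it through.** **1. Is the comparison like for like?**

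| | Group 1 | Groups 2-4 |
|---|---|---|
| Socket content on day 0 (4.7) | no graft | packed to complete fill |
| Graft possible at 8 weeks (12.1, SA-5) | no | yes, and the plan measures it in the core |
| CBCT rule excluding graft (5.1, 8.1) | not needed | none stated |
| Value analysed in SA-4 (12.4) | 8 weeks only | 8 weeks only |

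Measured fill is new bone in Group 1. In Groups 2-4 it is new bone plus whatever residual graft the reading counts. The two agree only if that second term is zero or is removed.

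**2. The plan's own power figure.** Section 12.5 gives 52% power for SA-4. Inputs: 4 groups, effective n = 25 per group, two-sided 5%, and a medium effect, taken as Cohen's f = 0.25. The noncentrality is 4 × 25 × 0.25² = 6.25, with 3 and 96 degrees of freedom. The noncentral F distribution gives 51.8%, so the figure reproduces. At n = 20 per group (SA-5) the result is 42.0%, against 42% stated.

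**3. What an artefact would do to the SA-4 F-test.** The documents give no size for residual graft on CBCT, so this is an illustration over an assumed range. Suppose true new bone is equal in all four groups and residual graft raises measured fill in Groups 2-4 by b sd. The grand mean is 0.75b, so the noncentrality is n × [(0.75b)² + 3 × (0.25b)²] = 0.75 × n × b².

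| b (sd) | Noncentrality, n = 25 | Chance of a significant F-test, n = 25 | Same, n = 20 |
|---|---|---|---|
| 0 | 0 | 5% | 5% |
| 0.25 | 1.17 | 12.5% | 10.8% |
| 0.50 | 4.69 | 40% | 32% |
| 0.75 | 10.55 | 77% | 66% |
| 1.00 | 18.75 | 96% | 90% |

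The rate rises with n, so a larger trial would not dilute the problem.

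**4. What the histology alternative can deliver.** For a pooled Groups 2-4 versus Group 1 contrast the noncentrality is d / √(1/n₁ + 1/n₂).
- Check against the plan: SA-1 with 25 v 75 and d = 0.5 gives 0.5 / √(1/25 + 1/75) = 2.17 on 98 df. Power is 57%, as section 12.5 states.
- Percent new bone: 20 v 60 and d = 0.5 gives 0.5 / √(1/20 + 1/60) = 1.94 on 78 df. Power is 48%.

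**The case against.** The strongest reply is that the trial already measures the right quantity elsewhere. Section 10.1 says histology will show whether the grafts promote new osseous tissue, with comparison between experimental groups and controls. SA-5 analyses percent new bone in all four groups with Tukey pairs. This stands: a valid graft-versus-control comparison of bone formation exists, and only a pooled contrast would be new. It does not repair SA-4, because nothing links the two aims or tells the reader which should carry the conclusion.

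Several stronger readings are tempting, and the documents do not support them:

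- **A reader might infer that the plan counts residual graft as bone.** No text says so. The instrument for SA-4 is inferred from 12.1, and image-reading rules could be in the Manual of Procedures (Appendix E), which was not available. What can be said is that no separating rule is stated.
- **A reader might attach a figure to the bias.** The documents give neither a residual-graft share nor a definition of how fill is scored, so the size is unknown.
- **A reader might conclude that Hypothesis II fails.** That hypothesis concerns adding growth factors to graft. Its main contrasts lie among Groups 2-4, which share a stated FDBA/TCP base and are less affected. They are not immune: graft resorption could differ between them, and step 4.7-4c refers to GEM-21S, which leaves the Group 4 mixture less clear than its 8:2 description and should be reconciled with it.
- **A reader might object that the first scan follows grafting, so change from baseline is not comparable.** SA-4 uses "mixed-model ANOVA and the 8 week measurement only", so this does not bear on it.

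**Conclusion.** The concern holds for the comparisons with control. As SA-4 is written, its overall F-test and its Tukey pairs against Group 1 can reflect the presence of graft rather than bone formation, in a direction that favours grafting. The size cannot be derived from the documents; the table shows only how the test would respond to a given shift.

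The conclusion rests on three assumptions: SA-4 fill is measured by CBCT, as 12.1 indicates; some residual graft is visible on CBCT at 8 weeks; and no separating rule exists outside the supplied text.

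The same concern may apply to the SA-2 bone-volume contrasts that involve Group 1, if bone volume there means CBCT fill within the socket, which is not stated. Histology limits the harm, so this is a point to correct in the plan and not a flaw in the trial as a whole.

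**What to change.** Changes to the wording of 12.1 and 12.4:

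1. In SA-4, name the instrument and call the endpoint radiopaque (mineralised) fill, including residual graft. Do the same in SA-2 if its bone volume is CBCT fill within the socket. If the Manual of Procedures already separates graft from bone, cite that rule instead.
2. Correct qualitative to quantitative in the SA-4 analysis sentence.
3. State that comparisons of this endpoint with Group 1, including a four-group F-test that may be driven by Group 1, are descriptive and are not evidence of new bone formation.
4. Name SA-5 percent new bone as the basis for conclusions on graft-versus-control bone formation, in line with 10.1. Add a pooled Groups 2-4 versus Group 1 contrast to the existing Tukey pairs.

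No new scan, procedure or participant is needed. The cost is precision: the comparison rests on one core from one site per participant (20 v 60), with about 48% power for a 0.5 sd difference. It also adds one prespecified test to SA-5.
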